			# of 10 and/or 20 mg tablets taken twice daily		
			10 mg	20 mg	
Day 1		AM			
		PM			
Day 2		AM			
		PM			
Day 3		AM			
		PM			
WEEK 2	Date	Time	# of 10 and/or 20 mg tablets prescribed to take		Comments (Describe any missed or extra doses, vomiting and/or bothersome effects.)
			10 mg	20 mg	
			AM# _____	AM# _____	
			PM# _____	PM# _____	
			# of 10 and/or 20 mg tablets taken twice daily		
			10 mg	20 mg	
Day 8		AM			
		PM			
Day 9		AM			

THIS PROTOCOL IS FOR RESEARCH PURPOSES ONLY, SEE PAGE 1 FOR USAGE POLICY

			PM			
Day 10			AM			
			PM			
WEEK 3	Date	Time	# of 10 and/or 20 mg tablets prescribed to take		Comments (Describe any missed or extra doses, vomiting and/or bothersome effects.)	
			10 mg	20 mg		
			AM# _____	AM# _____		
			PM# _____	PM# _____		
			# of 10 and/or 20 mg tablets taken twice daily			
	10 mg	20 mg				
Day 15		AM				
		PM				
Day 16		AM				
		PM				
Day 17		AM				
		PM				
WEEK 4	Date	Time	# of 10 and/or 20 mg tablets prescribed to take		Comments (Describe any missed or extra doses, vomiting and/or bothersome effects.)	
			10 mg	20 mg		
			AM# _____	AM# _____		
			PM# _____	PM# _____		
			# of 10 and/or 20 mg tablets taken twice daily			
	10 mg	20 mg				
Day 22		AM				
		PM				
Day 23		AM				
		PM				
Day 24		AM				
		PM				

If this form will be used as a source document, the site personnel who administered the study drug must sign and date this form below:

Signature: _____ Date: _____
(site personnel who reviewed the diary)

APPENDIX VIII: BIOMARKER STUDIES

Phase 1 (Part A):

Time Point	Specimen and Quantity	Send Specimens to:
Baseline		
	
 • 1 Archival FFPE tumor block or 1-2 unstained slides of archival tumor tissue samples for ATM IHC (Required)¹ • 1 Archival FFPE tumor block (can be the same block as previous bullet) or 5-8 unstained slides for other IHC studies (Optional)¹ • 1-2 snap-frozen tumor blocks of any size¹ (optional size for WGS and ALT (Optional)² • 2-4 mL blood in purple top EDTA tube for control blood (Optional)³ 	[name]
	
 • ~10 mL plasma in purple top EDTA tube for ALT ctDNA (Optional) 	[name]
	
 • Archival FFPE tumor block or 1 H&E stained slide (3-5 µm) and 10 unstained, uncharged, air-dried slides (10 µm) (Optional) 	Biopathology Center Nationwide Children's Hospital
Cycle 1, Day 1		
	
 • 5-10 mL blood in purple top EDTA tube for five required PK levels (Required) • 1-2 mL blood in purple top EDTA for 12 hour trough PK levels(Optional) 	[name]
Cycle 1, Day 3		
	
 • 2-4 mL blood in purple top EDTA tube (Required) 	[name]
Cycle 1, Day 10		
	
 • 5-10 mL blood in purple top EDTA tube for five required PK levels (Required) • 1-2 mL blood in purple top EDTA for 12 hour trough PK levels(Optional) 	[name]
Any biopsy occurring on-study or within 30 days of end-of treatment		
	
 • Archival FFPE tumor block or 2up to 10 unstained slides, cut into 5 micron sections for each slide (optional) • 1 snap-frozen tumor block of any size (optional) 	[name]

¹FFPE tumor blocks can be used as an alternative for unstained slides²Ideally 1 from diagnosis, 1 from relapse

THIS PROTOCOL IS FOR RESEARCH PURPOSES ONLY, SEE PAGE 1 FOR USAGE POLICY

³Control blood for WGS is collected once at any time, but preferably at the same time as the frozen tumor blocks

Phase 2 (Part B):

Time Point	Specimen and Quantity	Send Specimens to:
Baseline		
	
 • 1 Archival FFPE tumor block or 1-2 unstained slides of archival tumor tissue samples for ATM IHC (Required)¹ • 1 Archival FFPE tumor block (can be the same block as previous bullet) or 5-8 unstained slides for other IHC studies (Optional)¹ • 1-2 snap-frozen tumor blocks of any size for WGS and ALT (Optional)² • 2-4 mL blood in purple top EDTA tube for control blood (Optional)³ 	[name]
	
 • ~10 mL plasma in purple top EDTA tube for ALT ctDNA (Optional) 	[name]
	
 • Archival FFPE tumor block or 1 H&E stained slide (3-5 µm) and 10 unstained, uncharged, air-dried slides (10 µm) (Optional) 	Biopathology Center Nationwide Children's Hospital
Cycle 1, Day 1		
	
 • 2-4 mL blood in purple top EDTA tube for PK levels (Required) 	[name]
Cycle 1, Day 3		
	
 • 2-4 mL blood in purple top EDTA tube for PK levels (Required) 	[name]
Cycle 1, Day 10		
	
 • 2-4 mL blood in purple top EDTA tube for PK levels (Required) 	[name]
Any biopsy occurring on-study or within 30 days of end-of treatment		
	
 • Archival FFPE tumor block or up to 10 unstained slides, cut into 5 micron sections for each slide (optional) • 1 snap-frozen tumor block of any size (optional) 	[name]

¹FFPE tumor blocks can be used as an alternative for unstained slides

²Ideally 1 from diagnosis, 1 from relapse

³Control blood for WGS is collected once at any time, but preferably at the same time as the frozen tumor blocks

APPENDIX IX: CORRELATIVE STUDIES GUIDE

Correlative Studies	Appx.	Volume per Sample (ml)	Total Volume (ml)
ATM Tumor Tissue	2	0	0
Tumor Whole Genome Sequencing Tumor Tissue	3	0	0
Tumor Whole Genome Sequencing Control Blood	1	2-4 mL	2-4 mL
R-Loops & PGBD5 Tumor Tissue	1	0	0
pH2AX, pKAP1 and pATR Tumor Tissue	1-2	0	0
Circulating tumor DNA to evaluate for ALT	1	~10 mL	~10 mL
Archival Tumor Tissue for Biobanking	1	0	0
Required Pharmacokinetics for Patients on Part A	12	~2	~24
Required Pharmacokinetics for Patients on Part B	6	~2	~12
Optional Pharmacokinetics for Patients on Part A	2	~2	~4
Total Blood Volume =			~52-54 mL

Priority	Biomarker Name	Assay (CLIA : Y/N)	Use in the Trial (Integral, Integrated, or Exploratory) AND Purpose	Specimens Tested	Collection Time Points	Mandatory or Optional	Assay and Lab PI ^c
Tissue-based Biomarkers							
1	ATM	IHC CLIA: N	Exploratory Correlative See section 8.6.1 for purpose.	FFPE Tumor	Pre-dose, archival tumor tissue, post treatment study	M	[name] (MSKCC, New York City, NY) [contact]

Priority	Biomarker Name	Assay (CLIA : Y/N)	Use in the Trial (Integral, Integrated, or Exploratory) AND Purpose	Specimens Tested	Collection Time Points	Mandatory or Optional	Assay Laboratory and Lab PI ^c
2	Tumor Whole Genome Sequencing	Whole Genome Sequencing CLIA: N	Exploratory Correlative See section 8.3.1 for purpose.	Frozen Tumor	Pre-dose, archival tumor tissue, at relapse, post treatment study	O	[name] (MSKCC, New York City, NY) [contact]
3*	pH2AX, pKAP1 and pATR	IHC CLIA: N	Exploratory Correlative See section 8.3.3 for purpose	FFPE Tumor	Pre-dose, archival tumor tissue	O	[name] (MSKCC, New York City, NY) [contact]
4*	R-loops PGBD5	IHC CLIA: N	Exploratory Correlative See section 8.3.2 for purpose	FFPE Tumor	Pre-dose, archival tumor tissue	O	[name] (MSKCC, New York City, NY) [contact]
5	ALT RT-PCR for TERT and C-circle assay	RT-PCR for TERT and C-circle assay CLIA: N	Exploratory Correlative See section 8.3.1 for purpose	FFPE Tumor	Pre-dose archival tumor tissue, post-dose (Analyzed with WGS tumor tissue)	O	[name] [name] (COGCCXR, Lubbock, TX) [contact]
6.	Archival Tumor Tissue for Biobanking	Archival Tumor Tissue CLIA: Y	Exploratory Correlative See Section 8.3.6	FFPE Tumor slides	Pre-dose archival tumor tissue	O	Biopathology Center Nationwide Children's Hospital [contact]
Blood-based Biomarkers							
1	ALT	ctDNA CLIA: N	Exploratory Correlative See section 8.3.4 for purpose	Blood (pre-dose)	Pre-Dose	O	[name] [name] (COGCCXR, Lubbock, TX) [contact]

Priority	Biomarker Name	Assay (CLIA : Y/N)	Use in the Trial (Integral, Integrated, or Exploratory) AND Purpose	Specimens Tested	Collection Time Points	Mandatory or Optional	Assay Laboratory and Lab PI ^c
2	ALT	RT-PCR for TERT and C-circle assay CLIA: N	Exploratory Correlative See section 8.3.1 for purpose	Blood (pre-dose)	Pre-Dose (Analyzed with WGS blood samples)	O	[name] [name] (COGCCXR, Lubbock, TX) [contact]
2	Tumor Whole Genome Sequencing	Whole Genome Sequencing CLIA: N	Exploratory Correlative See section 8.3.1 for purpose.	Blood (pre-dose)	Pre-Dose	O	[name] (MSKCC, New York City, NY) [contact]
3.	Pharmacokinetics	Pharmacokinetics CLIA: Y	Integrated Correlative See section 8.5.1 for purpose	Blood	Part A: Cycle 1, Day 1; Cycle 1, Day 3; Cycle 1, Day 10 Part B: Cycle 1, Day 1; Cycle 1, Day 3; Cycle 1, Day 10	M	[name] Pharmacology Shared Resource [contact]
4.	Pharmacokinetics	Pharmacokinetics CLIA: Y	Exploratory Correlative	Blood	Part A: Cycle 1, Day 1; Cycle, 1, Day 10	O	[name] Pharmacology Shared Resource [contact]

* Will prioritize pH2AX, pKAP1 and pATR over R-loops and PGBD5 if there are pre-/post- matched samples. If not, will prioritize R-Loops and PGBD5.

THIS PROTOCOL IS FOR RESEARCH PURPOSES ONLY, SEE PAGE 1 FOR USAGE POLICY

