1.2 Secondary Aims

1.2.1 To characterize the pharmacokinetics of BAY 1895344 (elimusertib) in children and adolescents with recurrent or refractory cancer.

1.2.2 To assess the biologic activity of BAY 1895344 (elimusertib) by immunohistochemical assessments of pATR, pH2AX, and pKAP1 in paired tissue samples before and after treatment with BAY 1895344 (elimusertib).

1.2.3 To assess whether the activity of BAY 1895344 (elimusertib) is influenced by ALT, as well as tumor tissue expression of ATM, PGBD5, and/or R-loops.

1.2.4 To assess whether the activity of BAY 1895344 (elimusertib) is associated with tumor mutational processes, as measured by whole genome tumor tissue sequencing.

1.2.5 To preliminary determine the anti-tumor activity of BAY 1895344 (elimusertib) in children < 18 years of age within the confines of a phase 1 study (Part A).

Phase 2 Secondary Aims

1.2.6 To assess the antitumor activity of BAY 1895344 (elimusertib) in pediatric patients with non-CNS solid tumors or lymphomas with specific deleterious alterations in DDR pathway genes.

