ATM kinase phosphorylates histone H2AX (pH2AX) at the site of DNA damage where it acts as a scaffolding for the assembly of repair machinery.³⁷ KAP1, another phosphorylated substrate of ATM, is a co-repressor for Kruppel-associated box zinc finger proteins that bind to and repress DNA through their zinc fingers.³⁷ Replication stress and more broadly DNA damage, are commonly measured by the presence of pH2AX and pKAP1.^{11,37} In this study, pH2AX and pKAP1 as well as the activated pATR will be evaluated in matched pre- and post- treated tumor samples, where available, in order to evaluate the impact of BAY 1895344 (elimusertib) on DNA damage repair.

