k. Study specific prior therapy: Patients must not have received prior exposure to BAY 1895344 (elimusertib) or any other specific ATR inhibitors including Berzosertib (M6620, VX-970), Ceralasertib (AZD6738), M4344 (VX-803), M1774, and RP-3500. Treatment with other DNA damage repair inhibitors which do not specifically inhibit ATR (e.g., PARP inhibitors, WEE1 inhibitors, CHEK1 inhibitors, etc.) does not exclude them from eligibility on this study.

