Immunohistochemistry for pH2AX, pKAP1 and pATR will be performed on pre- and, where available, post- treatment tumor samples. These studies will primarily investigate whether treatment with BAY 1895344 (elomusertib) increases pH2AX and pKAP1 and decreases pATR and thus supports the proposed mechanism of DNA damage repair inhibition and ATR inhibition. Secondarily, we will evaluate whether pH2AX and pKAP1 and pATR are expressed at baseline in certain pediatric tumors.

8.3.3.1 **Sampling Schedule**

- Prior to the start of therapy
- With any biopsy occurring on-study or within 30 days of end-of treatment.

8.3.3.2 **Sample Collection and Handling Instructions**

A minimum of 1 and a preference of 2, unstained slides of FFPE tumor tissue samples will be obtained at the above time points for pH2AX, pKAP1 and pATR, respectively. An FFPE tumor block instead would also be sufficient.

8.3.3.3 **Sample Processing**

Samples can be processed at any institution and either slides or blocks may be sent. Both slides and blocks can be stored prior to shipment, refrigerated at 4 °C.

If sending slides, cut tumor into 5 µm sections and place, unstained, on a positive glass slide for conventional IHC (Superfrost plus slides are recommended). Place the slide holder in a Zipper lock bag and eliminate as much air (and therefore moisture) as possible prior to sealing the bag.

FFPE tumor blocks may alternatively be sent to the [name] lab if preferable. If sending a block, aim to submit a piece approximately 0.5-1 cm³. After cutting an appropriately sized FFPE tumor block, place appropriate sample ID label onto the back of the cassette then place labeled cassette in a Zipper lock bag.

8.3.3.4 **Sample Shipping Instructions**

Samples will be kept cold using ice packs with overnight delivery to the address below. Include the corresponding copy of the completed PEPN2112 Tumor Tissue for Immunohistochemistry pH2AX, pKAP1 and pATR Transmittal form (from RAVE) with each shipment.

[name]

THIS PROTOCOL IS FOR RESEARCH PURPOSES ONLY, SEE PAGE 1 FOR USAGE POLICY

[name] Research Group
[name]
[name]

[contact]
E-mail: [contact]

Please include qualifying genomic testing report.

Friday collections are not permitted. Deliveries will be accepted Tuesday through Friday. Saturday and holiday shipments are not accepted. Please contact lab, prior to shipping.

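### The optional paired pATR/pH2AX/pKAP1 study permits a baseline block that predates other anti-cancer therapy, so in such pairs a change cannot be attributed to elimusertib alone

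*Combined protocol and SAP*

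**What the plan says.** Secondary aim 1.2.2 assesses biologic activity from pATR, pH2AX and pKAP1 in tissue taken before and after elimusertib. Section 8.3.3 states the main question: whether treatment "increases pH2AX and pKAP1 and decreases pATR and thus supports the proposed mechanism of DNA damage repair inhibition and ATR inhibition". Its secondary question is whether the markers are expressed at baseline in certain pediatric tumors.

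For the baseline sample, Section 8.3.3.1 says only "Prior to the start of therapy". Appendix VIII asks at baseline, in Part A and Part B alike, for "1 Archival FFPE tumor block (can be the same block as previous bullet) or 5-8 unstained slides for other IHC studies". The Appendix IX row for these markers reads "Pre-dose, archival tumor tissue". The later sample may come from any on-study biopsy, or from one within 30 days after treatment ends (8.3.3.1).

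Section 11.12 plans descriptive summaries of the biomarkers and calls them exploratory. It does not separate pairs by the date of the baseline tissue or by therapy given since.

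**The concern.** A before/after difference speaks to a drug only if the drug is the main thing that happened between the two samples. In this population much else can happen. A block from first diagnosis meets the stated requirement, and the patient may since have had several lines of DNA-damaging treatment and a relapse. In such a pair a rise in pH2AX or pKAP1 could reflect earlier therapy or a changed tumor. Conversely, a block taken soon after DNA-damaging treatment could start high and hide a real effect of elimusertib.

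At stake is the mechanism statement under aim 1.2.2. There is also a smaller practical consequence. The note in 8.3.3 and the footnote to Appendix IX give these markers priority for tissue over R-loops and PGBD5 when matched samples exist, but no section says what makes a pair matched.

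**Working it through.** The plan gives no sample size, test or expected effect for this analysis, so there is no figure to reproduce. The check is a comparison of sections.

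1. **Is old tissue permitted?** Yes. Section 8.3.3.1 sets no time window, and both appendices name archival tissue. If the Appendix IX entry is read as two alternatives (pre-dose tissue, or archival tissue), archival tissue is still one of them. Section 4.1.5 accepts histology from first diagnosis or from relapse, and Section 4 does not require a biopsy at study entry.

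2. **Can other therapy fall between the block and the first dose?** Yes. Section 4.1.10.1 allows earlier myelosuppressive chemotherapy (at least 21 days before enrollment, 42 after a nitrosourea) and local radiation (at least 14 days). Under item k, earlier treatment with PARP, WEE1 or CHEK1 inhibitors "does not exclude them from eligibility on this study". These intervals run from the last treatment to enrollment and do not constrain when the block was taken.

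3. **Are the markers specific to elimusertib?** Not on the protocol's own account. The section on pharmacodynamic biomarkers (2.2.3) says: "Replication stress and more broadly DNA damage, are commonly measured by the presence of pH2AX and pKAP1". It makes no such general statement about pATR.

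4. **What does the paired change contain?** Let B be the marker value in the baseline block, F the value at the first elimusertib dose and A the value in the later sample. Then

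 A − B = (A − F) + (F − B).

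 Only A − F covers the period on elimusertib. If the block was taken after the last prior therapy and close to the first dose, F − B should be small. If therapy intervened, F − B is unknown, because F is not observed. Averaged over all pairs, the unwanted part is the share of pairs with intervening therapy times the mean F − B in those pairs, taking F − B as about zero in the others. The documents give neither quantity, so size and sign both stay open.

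5. **Does the analysis separate the two kinds of pair?** No. Section 11.12 would pool them.

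6. **Does the protocol use a safeguard elsewhere?** Yes, for whole genome sequencing. Section 8.3.1.1 distinguishes diagnosis, relapse and post-treatment samples, and 8.3.1.2 asks for the collection date and time of the tissue. Section 8.3.3 asks for neither.

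**The case against.** The strongest reply is that the plan already gives this work little weight. It is optional, labelled exploratory, limited to available tissue and summarized descriptively; no dose, safety or response conclusion uses it. That stands, and it limits the importance of the point. It does not remove the problem, because describing a mixed set of pairs does not separate their causes, and 8.3.3 still plans to read the change as support for the mechanism.

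A reader might infer that the appendices require old tissue. They do not. The 8.1 schedule and the 8.3.3 title say only tumor tissue, whereas the PGBD5/R-loop entries say archival. Appendix VIII even applies the word archival to blocks from on-study biopsies. Archival tissue is permitted, and a recent sample may be sent.

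A reader might also infer that the paired change says nothing about elimusertib, or that the bias can be sized. Neither is supported. Earlier specific ATR inhibitors are excluded, so prior ATR inhibition is not a competing explanation. The washouts plus time on study may let short-lived effects of prior therapy fade. No section says how long such treatments shift these markers, or what tumor evolution does to them.

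It is also fair to say that restricting the baseline alone would not isolate the drug, since the later sample is untimed. Section 2.3.3 gives an adult terminal half-life of 11.5 hours. A sample at 30 days after the last dose (30 × 24 = 720 hours) lies 720 / 11.5 ≈ 63 half-lives out. That stands, and the fix therefore covers the timing of the later sample.

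Finally, the transmittal form and case report forms are not in the documents, so it cannot be said that the collection date and prior therapy go unrecorded.

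**Conclusion.** The point holds as a limited one. The plan permits baseline tissue that predates other anti-cancer therapy, and it pools such pairs with clean ones behind a statement about elimusertib's mechanism. In the affected pairs a change cannot be attributed to elimusertib alone.

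The conclusion assumes that some submitted baselines will be older blocks followed by further therapy. The plan allows this, but the documents do not say how often it will occur. Nothing in the primary aims is affected. This is a worthwhile, low-cost improvement to a named secondary aim.

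**What to change.** - **Section 8.3.3.1:** request the most recent pre-treatment tissue available. Make sure that its collection date, and any anti-cancer therapy between collection and the first elimusertib dose, are linked to the sample. If the existing forms already capture both, a cross-reference is enough.
- **Section 11.12:** base the statement that the change supports the mechanism on pairs with no anti-cancer therapy between the baseline sample and the first dose. A sample from the current relapse qualifies only if no therapy followed it. List the other pairs separately, and show the time from the last elimusertib dose to the later sample.
- **Appendix IX:** add the post-treatment time point to the row for these markers, to agree with 8.1 and 8.3.3.1. State there what counts as a matched pair.

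Older blocks remain usable for the baseline-expression question in 8.3.3. The cost is some wording and, at most, two form fields; no patient needs another biopsy. The drawback is that fewer pairs will support the main statement, in a set that already depends on whatever tissue is available.

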APPENDIX X: PART A PHARMACOKINETIC WORKSHEET (SAMPLE)

COG Pt ID # _____

Please do not write patient names on this form or on samples.

Patient BSA: _____ m² Dose: _____ mg/m² Dose given prior to PK sampling: _____ mg

Blood samples will be collected in consenting patients in EDTA tubes at the following time points:

Peripheral blood samples for PK analysis should be obtained as follows:

Record the exact date and time the sample is drawn.

Sample ID	Time Point	Scheduled Collection Time	Actual Date Sample Collected	Actual Time Sample Collected (24-hr clock)
1	Cycle 1, Day 1	Pre-dose	____ / ____ / ____	____ ____ : ____ ____
2	Cycle 1, Day 1	1 hour post-dose (± 15 minutes)	____ / ____ / ____	____ ____ : ____ ____
3	Cycle 1, Day 1	2 hours post-dose (± 15 minutes)	____ / ____ / ____	____ ____ : ____ ____
4	Cycle 1, Day 1	4 hours post-dose (± 15 minutes)	____ / ____ / ____	____ ____ : ____ ____
5	Cycle 1, Day 1	8 hours post-dose (± 30 minutes)	____ / ____ / ____	____ ____ : ____ ____
6	Cycle 1, Day 1*	12 hours post-dose (± 30 minutes)	____ / ____ / ____	____ ____ : ____ ____

BAY 1895344 (elimusertib) BID Dose on Cycle 1, Day 1	Date: ____ / ____ / ____	Time Dose Given: ____ : ____	Dose Given: _____ mg
---	--------------------------	---------------------------------------	----------------------

Sample ID	Time Point	Scheduled Collection Time	Actual Date Sample Collected	Actual Time Sample Collected (24-hr clock)
7	Cycle 1, Day 3	Pre-dose (within 1 hour before AM dose)	____ / ____ / ____	____ ____ : ____ ____
8	Cycle 1, Day 3	1 hour post-dose	____ / ____ / ____	____ ____ : ____ ____

BAY 1895344 (elimusertib) BID Dose on Cycle 1, Day 3	Date: ____ / ____ / ____	Time Dose Given: ____ : ____	Dose Given: _____ mg
---	--------------------------	---------------------------------------	----------------------

Sample ID	Time Point	Scheduled Collection Time	Actual Date Sample Collected	Actual Time Sample Collected (24-hr clock)
9	Cycle 1, Day 10	Pre-dose (within 1 hour before AM dose)	____ / ____ / ____	____ ____ : ____ ____
10	Cycle 1, Day 10	1 hour post-dose (± 15 minutes)	____ / ____ / ____	____ ____ : ____ ____
11	Cycle 1, Day 10	2 hours post-dose (± 15 minutes)	____ / ____ / ____	____ ____ : ____ ____
12	Cycle 1, Day 10	4 hours post-dose (± 15 minutes)	____ / ____ / ____	____ ____ : ____ ____

THIS PROTOCOL IS FOR RESEARCH PURPOSES ONLY, SEE PAGE 1 FOR USAGE POLICY

13	Cycle 1, Day 10	8 hours post-dose (\pm 30 minutes)	____/____/____	____ ____:____ ____
14	Cycle 1, Day 10*	12 hours post-dose (\pm 30 minutes)	____/____/____	____ ____:____ ____
BAY 1895344 (elimusertib) BID Dose on Cycle 1, Day 10		Date: ____/____/____	Time Dose Given: ____ ____:____ ____	Dose Given: _____ mg

*12-hour PK collection on cycle 1, day 1 and cycle 10, day 1 is optional, and if obtained, should be drawn before the PM dose.

One copy of this PK Form should be uploaded into RAVE. A second copy should be sent with the samples to the address listed in [Section 8.5.2](#), in addition to detailed guidelines for packaging and shipping PK samples.

If this form will be used as a source document, the site personnel who collected the samples must sign and date this form below:

Signature: _____
(site personnel responsible for collection of samples)

Date: _____

THIS PROTOCOL IS FOR RESEARCH PURPOSES ONLY, SEE PAGE 1 FOR USAGE POLICY

